# 10.1.3. Relationship of Adverse Event to Study Drug

Treatment-emergent adverse events with closest relationship to study drug according to the categories specified in the protocol (Not Related, Unlikely Related, Possibly Related, Related and Definitely Related) will be summarized for related and non-related events by SOC, PT, and treatment group.

A study drug related AE is defined as any AE that is assessed by the investigator with the relationships of "Possibly Related", "Related" and "Definitely Related". Study drug non-related AE is defined as any AE that assessed by investigator with the relationships of "Not Related" and "Unlikely Related".

Any treatment-emergent AEs that have a missing relationship will be presented as "Related" in the summary table but will be presented with a missing relationship in the data listing.

#### 10.1.4. Severity of Adverse Event

Treatment-emergent adverse events with maximum investigator-reported severity (mild, moderate, severe) will be summarized by SOC, PT, and treatment group.

Any treatment-emergent AEs that have a missing severity will be presented with the worst severity in the summary table but will be presented with a missing severity in the data listing.

#### 10.1.5. Serious Adverse Events

All treatment-emergent SAEs will be summarized by SOC, PT, and by treatment group.

A summary of study drug related treatment-emergent SAEs by SOC, PT, and treatment group will also be presented.

## 10.1.6. Adverse Events Leading to Study Drug Discontinuation / Study Termination

All treatment-emergent adverse events that lead to study drug discontinuation or study termination will be summarized by SOC, PT, and by treatment group.

# 10.2. Ocular Safety Assessments

Specific ocular safety assessments include intraocular ocular pressure, dilated ophthalmoscopy and corneal pachymetry. Specific ocular safety assessments will be summarized on the Safety analysis set by visit for descriptive statistics only. The descriptive statistics summary will be performed separately on the study eye and on the non-study eye where it is applicable. No statistical treatment group comparison will be performed. Unless otherwise noted, unscheduled and early termination visits will be assigned to an unplanned study visit using the analysis windows described in SAP Section 3.2.9 (Table 3) in case the scheduled visit was not performed.

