6.1 Inclusion Criteria

All subjects entered into this trial must meet the following criteria:

- 1. Subject is willing and able to comply with the protocol requirements, has gone through the consent process and has signed an approved informed consent form.
- 2. Male or female subjects aged ≥ 18 years and ≤ 85 years.
- 3. Subjects with acute endogenous non-infectious anterior uveitis with onset of symptoms within the previous 2 weeks.* Subjects experiencing a bilateral episode of anterior uveitis may be eligible for study in both eyes. Evaluations for selective infectious etiologies, including but not limited to Syphilis, Tuberculosis (if indicated), Herpes Simplex, Herpes Zoster, CMV, Lyme Disease or other suspected infectious etiology, must be performed during the screening period or within 3 months of randomization.
- 4. Presence of 6-50 anterior chamber cells within one field of view as measured with a slit lamp microscope (Grade 1+ to Grade 3+, Appendix 1) in the study eye(s).
- 5. Subjects must have pachymetry corrected IOP <21 mmHg at baseline and nonglaucomatous cups in the opinion of the investigator with non-glaucomatous visual fields if available, and may only administer a maximum of 1 topical medication to control IOP in the study eye.
- Best corrected visual acuity (BCVA) better than or equal to 35 letters in the study eye and 65 letters in the non-study eye using ETDRS testing. Note: this criteria is also applicable for a subject with bilateral uveitis.
- 7. Females of childbearing potential must be using or willing to use a medically acceptable method (as defined by the Investigator) of birth control. Women not of childbearing potential are defined as women who are either surgically sterile or postmenopausal.

Postmenopausal women are defined as women with cessation of menstruation for 12 consecutive months prior to signing of the informed consent form.

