*A history of prior flare-ups or subsequent flare-ups in the non-study eye should not affect eligibility, provided that the subject is deemed capable of administering separate treatments to each eye. For example, if an enrolled subject experiences a flare-up in the non-study eye, the subject should remain in the study, and the non-study eye should receive the standard of care treatment. Likewise, if a potential subject was already receiving standard of care treatment in the non-study eye prior to enrollment, the second eye is eligible for the study and the non-study eye will continue to receive the standard of care.

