6.2 Exclusion Criteria

Subjects will be excluded from this trial if they meet any of the following criteria:

- 1. Have severe/serious ocular pathology in the study eye(s) which may preclude study completion, in the judgement of the Investigator.
- 2. Any medical condition or clinical laboratory test which in the judgment of the Investigator makes the subject unsuitable for the study.
- 3. Currently or within past 5 years, have a history of malignancy other than successfully treated squamous or basal cell carcinoma of the skin or successfully treated in situ cervical cancer.
- 4. Active intermediate or posterior uveitis in the study eye(s). Note: a subject with isolated macular edema without evidence of active intermediate or posterior uveitis is eligible for enrolment.
- 5. Known or observed mild to severe (1-4+) fibrinoid reaction.
- 6. Previous anterior uveitis episode in the study eye ≤ 4 weeks prior to Visit 1.
- 7. Cataract and intraocular lens (IOL) implantation surgery or corneal transplantation in the study eye(s) within the past 3 months prior to Visit 1, or subjects who may require penetrating intraocular surgery in the study eye(s) during the study.
 - Subjects who are 3 months past uncomplicated cataract and IOL implantation surgery and have shown documented complete clearing of inflammation post-surgery in the study eye(s) are eligible.
 - Any other penetrating intraocular surgery in the study eye(s) within 3 months prior to Visit 1 are eligible, assuming documented complete clearing of inflammation post-surgery in the study eye(s).
- 8. Oral corticosteroid within the past 14 days prior to Visit 1.

- Topical ocular corticosteroid treatment in the study eye within the past 14 days prior to Visit 1 (Maximum of 3 doses of topical ocular steroid in the study eye in the 7 days prior to Visit 1 is permitted).
- 10. Intravitreal corticosteroid treatment in the study eye within the past 4 months prior to **Visit 1**.
- Sub-Tenon corticosteroid treatment in the study eye within the past 3 months prior to Visit 1.
- 14. Prescribed nonsteroidal anti-inflammatory agents or immunosuppressive agents, unless the dose has been stable for the last 6 weeks prior to Visit 1 and no change in dosing is anticipated for the duration of the study.

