#### **3.2.7. Study Eye**

A study eye will be determined at the Screening Visit as follows: If only one eye qualifies for treatment, that eye will be the study eye. If both eyes qualify for treatment, the eye with the higher anterior chamber cell score will be the study eye; or if both have the same score, the right eye will be the study eye. Although it is possible for the subjects who are experiencing a bilateral episode of anterior uveitis be treated in both eyes, the study eye will be used as the primary eye in the analyses.

Final 1.0

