#### 10.1. Adverse Events

Adverse events will be coded using MedDRA version 19.0. If a subject experiences multiple events that map to a single preferred term, the greatest severity and strongest investigator assessment of relationship to study drug will be reported for the applicable summaries.

Treatment-emergent adverse events (TEAE) are defined as events for which the date/time of onset is on or after the date of first dose of study drug. Where an AE with a partially or fully missing start date or time, and it is unclear as to whether the AE is treatment emergent, it will assume treatment emergent unless the CRF question "Did AE onset occur before the first dose of study drug (Yes/No)?" indicates otherwise.

The number and percentage of subjects with adverse events will be summarized by treatment group. System organ class will be sorted alphabetically and preferred term within each SOC will be sorted by overall descending order of frequency. Subjects will be counted only once for each SOC and PT. The percentages will be calculated based on the number of subjects in each treatment group of the Safety analysis set.

Final 1.0 March 13, 2019 Ocular and non-ocular adverse events will also be summarized.

All adverse events (treatment-emergent and non-treatment-emergent) will be listed.

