#### 10.2.1. Intraocular Pressure Measurement

The IOP is measured on both eyes (study and non-study eye) in millimeter of mercury (mm Hg) at Day 1 (Screening), Day 4, Week 1, Week 2, Week 3 and Week 4.

Descriptive summaries of the observed values at each scheduled visit as well as the change from baseline at each post-baseline visit will be presented for both eyes, without imputation.

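### Ocular safety tables place the second dosed eye of bilateral subjects among undosed and standard-of-care fellow eyes, and ocular TEAE summaries do not separate dosed from undosed eyes

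*SAP*

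**What the plan says.** Protocol 6.1 allows bilateral enrolment: "Subjects experiencing a bilateral episode of anterior uveitis may be eligible for study in both eyes". Its footnote covers a different kind of fellow eye. If that eye flares during the study, "the non-study eye should receive the standard of care treatment", and an eye already under such treatment at entry continues with it.

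SAP 3.2.7 reduces each subject to one study eye: "If both eyes qualify for treatment, the eye with the higher anterior chamber cell score will be the study eye", with the right eye taken in a tie. The same section accepts that a bilateral subject may "be treated in both eyes, the study eye will be used as the primary eye in the analyses".

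SAP 10.2 carries this two-way label into ocular safety: "The descriptive statistics summary will be performed separately on the study eye and on the non-study eye where it is applicable". SAP 10.2.1 (IOP) and 10.2.2 (fundus) describe the two eyes as study and non-study, with no third category.

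For adverse events, SAP 10.1 counts each subject once per system organ class and preferred term, and adds: "Ocular and non-ocular adverse events will also be summarized". It plans no summary by eye. The AE items required by Protocol 9.2.1 (relationship, severity, duration, frequency, action, seriousness, outcome) do not include the affected eye.

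Two planned outputs identify bilateral subjects: the count treated in both eyes (SAP 6.1) and bilateral uveitis at baseline (SAP 7.1). Exposure is summarized for the study eye only (SAP 6.2.1).

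**The concern.** For a topical product, the ocular safety question is what happens in an eye that receives the drops. A single study eye is a sound device for efficacy, because it gives one observation per subject. As a safety classification it sorts eyes by that choice rather than by exposure. Some dosed eyes then fall outside the only table made up entirely of dosed eyes, and the table they enter mixes three exposures: study drug, standard of care, and neither.

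The adverse event side has a similar gap. The protocol expects fellow-eye flares, and such an event can carry the same preferred term as an event in a dosed eye. A count of ocular events per subject cannot tell them apart, although SAP 10.1.2 tests the more frequent terms between arms.

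**Working it through.** The plan gives no figure to reproduce here. The point rests on reading its sections together; the arithmetic only shows scale.

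**Step 1. Where each eye is tabulated under SAP 3.2.7 and 10.2**

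| Eye | Receives study drug? | IOP and fundus table |
|---|---|---|
| Study eye | Yes | Study eye |
| Second qualifying eye, treated | Yes | Non-study eye |
| Fellow eye on standard of care | No | Non-study eye |
| Other fellow eye | No | Non-study eye |

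No sensitivity table, exclusion or separate row is planned for the second line. No sentence states the pooling; it follows from the two sections together. Pachymetry is measured only at screening, so it carries no post-dose information and is unaffected.

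**Step 2. Number of eyes.** Inputs: 60 subjects per arm (SAP 2.3.6) and the share *b* dosed in both eyes, which the documents do not give; 5% to 20% is assumed.

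- Second dosed eyes per arm = 60 × *b* = 3, 6 and 12 for *b* = 5%, 10% and 20%.
- Share of all dosed eyes = 60*b* / (60 + 60*b*) = 3/63, 6/66 and 12/72 = 4.8%, 9.1% and 16.7%.

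**Step 3. What the pooled table would show.** Suppose, for illustration, a mean IOP change of 5 mmHg in second dosed eyes and none in other fellow eyes. The non-study-eye mean is 5 × *b* = 0.25, 0.5 and 1.0 mmHg.

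If standard-of-care eyes, a share *s* of all non-study eyes, showed the same change, the pooled mean would be 5(*b* + *s*), of which dosed eyes contribute *b*/(*b* + *s*). With *b* and *s* each between 5% and 20%, this runs from 0.05/0.25 = 20% to 0.20/0.25 = 80%. A shift in the non-study-eye table could not be assigned to either source.

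**Step 4. What the TEAE summaries would show.** Assume, for one preferred term, dosed-eye rates of 15% (ADX-102) and 5% (vehicle), and an independent fellow-eye rate of 10% in both arms. Each subject is counted once, so the reported rate is 1 − (1 − dosed-eye rate)(1 − fellow-eye rate):

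- ADX-102: 1 − 0.85 × 0.90 = 23.5%
- Vehicle: 1 − 0.95 × 0.90 = 14.5%

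The ratio falls from 3.0 to 1.6, and the difference from 10 to 9 percentage points. The Fisher tests in SAP 10.1.2 apply to terms with at least 10% occurrence in any treatment group, so fellow-eye events can also decide which terms are tested. All rates in this step are assumed.

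**The case against.** The strongest reply is that no general drug effect is hidden. Every treated subject contributes one dosed eye to the study-eye table, and no undosed eye enters it. An effect of the drops on IOP would appear there undiluted, in about 60 eyes per arm. A reader might infer from Step 3 that a safety signal would be lost. That would require the effect to occur in second dosed eyes and not in study eyes, and nothing in the documents suggests this. The reply stands, and it limits the point to information on the second dosed eyes themselves.

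A reader might also take the non-study-eye table to be a control that has been spoiled. The documents do not use it as one. The control is the randomized vehicle arm, SAP 10.2 rules out treatment comparisons for these tables, and no planned analysis sets study eye against non-study eye.

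It is tempting to call the standard-of-care eyes steroid-treated. The protocol names no agent. The relevant exclusion is worded for one eye only ("Topical ocular corticosteroid treatment in the study eye within the past 14 days prior to Visit 1"), so a topical steroid in the fellow eye is not ruled out, but that does not establish its use.

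On adverse events, SAP 10.1.3 tabulates related and non-related TEAEs, and investigators must weigh pre-existing conditions, concurrent medication and timing (Protocol 9.2.1). This separates events in part, but relatedness does not identify the eye. All adverse events are listed, and the eCRF is not among the documents, so laterality may be recorded. The gap is shown only for the planned summaries and for the protocol's list of AE items.

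The protocol's use of study eye(s) in 6.1 and 6.2, and the similar plural in SAP 7.1, could suggest that both dosed eyes count as study eyes. SAP 3.2.7 is singular and is the definition that the analysis uses. At best the label of the second eye is ambiguous, and the passages should be reconciled.

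**Conclusion.** The point holds in a limited form. The plan's own rules tabulate second dosed eyes with undosed and standard-of-care fellow eyes for IOP and fundus, and its ocular TEAE summaries do not distinguish dosed from undosed eyes. The study-eye tables and the primary efficacy analysis are unaffected. What is lost is a clear safety description of second dosed eyes, together with ocular TEAE rates free of fellow-eye events.

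The size is unknown because the documents give no bilateral share. At an assumed 5% to 20% of 60 per arm it is 3 to 12 eyes per arm. The SAP 6.1 count will show the actual number, but it does not separate those eyes in the safety tables. This is a cheap improvement to safety reporting and does not threaten the trial's conclusions.

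**What to change.** - **SAP 10.2 (IOP and fundus).** Report four categories: study eye; second dosed eye; undosed fellow eye on standard of care; undosed fellow eye without it. State how a fellow eye that starts standard of care during the study is classified, for example by its status at each visit.
- **Do not pool** the second dosed eye with the study eye. Pooling would put two correlated eyes from some subjects into one summary and give bilateral subjects double weight.
- **SAP 10.1.** Add a summary of ocular TEAEs in dosed eyes and in undosed eyes, using laterality from the AE form or the reported term. Count a subject once in each row that applies.
- **Labels.** Reconcile the plural study-eye wording in Protocol 6.1 and 6.2 and SAP 7.1 with the single study eye in SAP 3.2.7.
- **Leave unchanged** the single study eye for efficacy. Slit lamp and BCVA are planned as efficacy summaries (SAP 9.3.1 and 9.3.3), so there is no safety version of them to re-cut.

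The cost is SAP wording and a few table rows, some with small counts. IOP and fundus are already collected per eye, and subjects treated in both eyes are already to be counted. AE laterality must be captured if the form does not record it, and the standard-of-care split needs ocular concomitant medication records that identify the eye.

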#### 10.2.1. Intraocular Pressure Measurement

The IOP is measured on both eyes (study and non-study eye) in millimeter of mercury (mm Hg) at Day 1 (Screening), Day 4, Week 1, Week 2, Week 3 and Week 4.

Descriptive summaries of the observed values at each scheduled visit as well as the change from baseline at each post-baseline visit will be presented for both eyes, without imputation.

# 10.2.2. Dilated Ophthalmoscopy (Fundus Exam)

The dilated fundus exam is performed on both eyes (study and non-study eye) at Day 1 (Screening), Day 4, Week 1, Week 2, Week 3 and Week 4.

Number and percentage of subjects with observed values of Normal or Abnormal as well as the categorical shift from baseline at each post-baseline visit will be tabulated at each scheduled visit for both eyes. The percentages will be calculated based on the number of subjects at each visit in each treatment group of the Safety analysis set. The percentages on the shift will be calculated based on the number of subjects with both baseline and post-baseline values.

Descriptive summaries of the observed cup-to-disc ratio at each scheduled visit as well as the change from baseline at each post-baseline visit will be presented for both eyes, without imputation.

# 10.2.3. Corneal Pachymetry

Central corneal thickness will be measured by applanation ultrasound pachymetry on both eyes (study and non-study eye) in micrometer (um). For each measurement, the highest and lowest of five consecutive readings will be discarded, and the average of the remaining three will be recorded. Corneal pachymetry will be completed at Day 1 (Screening) only. The average value of the three measurements will be summarized by descriptive statistics for both eyes.

# 10.3. Laboratory Test and Other Safety Assessments

Laboratory test and other safety assessments will be summarized on the Safety analysis set by visit for descriptive statistics only. No statistical treatment group comparison will be performed. Unscheduled and early termination visits will not be assigned to an unplanned study visit using the analysis windows described in SAP Section 3.2.9 (Table 3). Early termination visit will be summarized separately from the Week 4 summary. Unscheduled visit will not be summarized but will be listed.

# 10.3.1. Clinical Laboratory Test

Blood samples for the clinical laboratory evaluations will be collected at Day 1 (Screening) and Week 4, and will include:

Hematology: hemoglobin, hematocrit, red blood cell (RBC) count, RBC morphology, white blood cell (WBC) count with differential, mean corpuscular volume (MCV), mean corpuscular hemoglobin (MCH), mean corpuscular hemoglobin concentration (MCHC), and absolute platelet count.

Serum Chemistry Profile: albumin, alkaline phosphatase, alanine aminotransferase (ALT; SGPT), aspartate aminotransferase (AST; SGOT), bilirubin (total and direct), blood urea nitrogen (BUN), calcium, carbon dioxide (CO2), chloride, creatinine, creatinine phosphokinase (CPK), glucose, phosphate, potassium, sodium, total protein, and uric acid.

Descriptive summaries of the observed test results at each scheduled visit as well as the change from baseline at each post-baseline visit will be presented without imputation. Number and percentage of subjects with normal range of Low, Normal, High categories as well as the categorical shift from baseline at each post-baseline visit will be tabulated at each scheduled visit. The percentages will be calculated based on the number of subjects at each visit in each treatment group of the Safety analysis set. The percentages on the shift will be calculated based on the number of subjects with both baseline and post-baseline values.

# 10.3.2. Specific Uveitis Diagnostic Test

During Screening only, the HLA-B27 (Human leukocyte antigen subtypes B\*2701-2759) uveitis-specific diagnostic test will be obtained in all subjects experiencing their first episode of anterior uveitis, or in subjects experiencing a repeat episode where prior tests of this nature have not been previously performed. The test results will be listed only.

#### 10.3.3. Urine Pregnancy Test

For women of childbearing potential, a urine pregnancy test will be performed at Day 1 (Screening) and Week 4. The test results will be listed only.

#### 10.3.4. Vital Signs

Vital signs, measured after at least 5 minutes of rest, will include seated systolic blood pressure (SBP), diastolic blood pressure (DBP), heart rate (HR), respiratory rate (RR), and body temperature and will be obtained at Day 1 (Screening) and Week 4.

Blood pressure (BP) results will be recorded in mmHg. HR will be measured in the radial artery in the dominant arm for 30 seconds and will be recorded as beats per minute (bpm). RR will be measured and recorded in breaths per minute. Body temperature (oral measurement) will be measured using a digital thermometer in Fahrenheit (°F).

Descriptive summaries of the observed values at each scheduled visit as well as the change from baseline at each post-baseline visit will be presented without imputation.

# 11. CHANGES FROM PROTOCOL-SPECIFIED ANALYSES

These following changes are made in the SAP from Protocol Version 4 (June 20, 2018).

Protocol Section 10.5 Analysis Populations defines the ITT population as "The intent-to-treat population (ITT) is the population of all subjects who are randomized into a treatment group." The decision was made by the sponsor that SAP Section 3.1.1 modifies the ITT definition to "the population of all subjects who are randomized into a treatment group and received at least one dose of study drug." All efficacy analyses will use the new ITT definition from the SAP instead of the definition stated in the Protocol.

Protocol Section 10.5 Analysis Populations PP population definition includes a clarification of "Significant protocol violations prior to being rescued may exclude a rescued subject from the PP." It was determined by the sponsor that this clarification to be removed from SAP Section 3.1.2.

